## 5. CONSIDERATIONS FOR DATA ANALYSES AND DATA HANDLING CONVENTIONS

### 5.1. Treatment Group Comparability

Initial analyses examining group differences for baseline variables will use cross-tabulation, ANOVAs, and examination of correlations between baseline variables and specified outcomes. For the purposes of evaluating the comparability of groups, a posterior probability of > 95% will constitute evidence for statistically reliable differences. Baseline or demographic variables on which group differences are detected (excluding stratification variables), and which are correlated with outcomes, meet the definition of confounders, and will result in two sets of analyses: one in which the relevant variable is included as a covariate, and one in which it is not. This will permit determination of the degree to which any group differences might confound conclusions regarding treatment.

## 5.2. Study Treatment & Sub-group Display Descriptors

Treatment Group Descriptions		
Protocol treatment arm	Data Displays for Reporting	
Treatment Arm	Treatment Arm	Order in TLF
Arm 1	HB-adMSCs 100MM	1
Arm 2	Placebo	2

Treatment comparisons will be displayed as follows using the descriptors as specified in the statistical analysis:

HB-adMSCs 100MM vs. Placebo

## 5.3. Baseline Definitions

For all endpoints, the baseline value will be the latest pre-treatment assessment visit with a non-missing value. i.e., If an assessment has been made both at screening visit (Visit 1), and Day 0, infusion 1 visit (Visit 2, Day 0), the value from the Day 0 visit is used as the baseline value. If the value measured at the Day 0 visit is missing and the assessment also has been made at screening, then the screening value is used as the baseline value.

Unless otherwise stated, if baseline data is missing, no derivation will be performed and baseline will be set to “missing”.

### 5.3.1. Change from Baseline

Definition	Reporting Details
Change from Baseline	= Post-Dose Visit Value – Baseline
% Change from Baseline	= $100 \times [(Post-Dose Visit Value – Baseline) / Baseline]$

**NOTES:**

- The baseline will be displayed along with Visit name on all summary displays.

## **5.4. Examination of Covariates, Other Strata and Subgroups**

### **5.4.1. Covariates and Other Strata**

Baseline will be included as a covariate in the efficacy analyses, wherever applicable. Stratification variables used at randomization (site, illness severity, pre-existing condition, ethnicity, age group) will be included as covariates.

### **5.3.2 Examination of subgroups**

Secondary analyses will evaluate heterogeneity of treatment effect as a function of gender, age, ethnicity and strata defined by pre-existing condition and illness severity. The approach to subgroup analyses will utilize skeptical, informative priors to increase the likelihood of future replication.

## **5.5. Multiple Comparisons and Multiplicity**

In keeping with sound Bayesian analytic principles, salient error rates/operating characteristics for confirmatory analyses in each component of the trial (provided in the sample size justification section) result from Monte Carlo simulation. Any secondary analyses for which issues of multiplicity might be a consideration will use weakly, informative priors to regularize all estimates. Means for these regularizing priors will be centered on the null hypothesis, with variances determined by the scale of the data and credible effects previously reported in the literature in the most closely analogous studies. Of note is the principle that the more informative the priors are (based on credible estimates of these effects), (1) the greater the degree of regularization, (2) the more conservative the estimates, and (3) the more likely the results are replicate outside of the current sample. Indeed for any observed results, the Bayesian approach makes it possible to determine the sensitivity of the results to prior assumptions; the degree of prior skepticism an observer would require before dismissing the estimated treatment effect. In the interest of transparency and reproducibility, the resulting reports will provide the specifications of Bayesian model priors used for all secondary analyses.

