Safety is assessed by primary and secondary endpoints. Primary safety endpoints include incidence of adverse and serious adverse events. Secondary safety endpoints include incidence of specific adverse events including serious infections, infusion-related reactions, hepatotoxicity, heart failure, and cytopenias. Clinically significant changes in laboratory values, vital signs, weight, and physical examination results will also be measured.

Clinical efficacy is assessed by primary and secondary endpoints. Primary endpoints include the change from baseline in inflammatory markers (IL-6, D-dimer, C Reactive protein), time to clearing PCR test, change from baseline oxygenation, and time to return to room air (RTRA). Secondary endpoints include change from baseline of chest x-ray, change from baseline of CT scan, change from baseline of clinical laboratory values, adverse and serious adverse events, change in exploratory markers, and change in ordinal scale.

Analysis Population

Safety: All subjects receiving at least one infusion will be included for safety analysis.

Efficacy: All subjects receiving all four infusions will be included for efficacy analysis.

Additional sub-analysis will be performed comparing subjects receiving any other experimental treatment for COVID-19, to those who are not, in the following items:

- Change from baseline oxygenation
- Change from baseline chest x-ray
- Change from baseline CT scan
- Time to clearing PCR test
- Change from baseline inflammatory markers (IL-6, D-dimer, C Reactive protein)
- Change from baseline in IL-10
- Change from baseline in CD4:CD8 ratio
- Change from baseline in CD3⁺CD56⁺
- Change from baseline in VEGF
- Change from baseline in the 7-point ordinal scale

Demographic and Baseline Characteristics

Information describing subjects' gender, race/ethnicity, and age will be displayed in tables similar to the ones included below. The number and percent of the total sample population will be calculated for each demographic category.

Demographics	Female		Male		Both Genders	
Race/Ethnicity	N	%	N	%	Total	%
White						
Black or African American						
Hispanic or Latino						
Other (Specify)						
Total						

The mean, minimum, and maximum age at enrollment will be determined using standard calculations. The number and percent of total subjects in each age group will be calculated and reported.

Age at Enrollment	N	%
Mean		
Minimum		
Maximum		
	N	%
≥ 18 years		
18-21 years		
22-29 years		
30-39 years		

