Evaluation of posterior distributions will permit statements regarding the probability that effects of varying magnitudes exist, given the data. Specification of diffuse, neutral priors will reflect the initial uncertainty regarding effect sizes. For all generalized linear models, priors for regression coefficients will be specified as  $\sim$ Normal ( $\mu=0$ ,  $\sigma^2=1 \times 10$ ), and priors for the levels one and two error variances will be specified as  $\sim$ Half-Normal ( $\mu=0$ ,  $\sigma^2=1 \times 10^3$ ). The choice of prior distribution for level two variances will follow Gelman's recommendations from the literature. Priors for the comparison of proportions will be specified as  $\sim$ Beta ( $\alpha=1.0$ ,  $\beta=1.0$ ).

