## 7.2. Secondary Efficacy Analyses

### 7.2.1. Endpoints / Variables

Change from baseline through Visit 5 (Day 10):

- Change in clinical laboratories
- Change from baseline in exploratory markers (D-dimer, myoglobin, troponin, creatinine kinase, serum ferritin, CD3CD56, CD4/CD8, VEGF)

Change from baseline through Visit 6 (Day 28):

- Change from baseline Chest X-ray (available at Visit 6 only)
- Change from baseline CT scan (available at Visit 6 only)
- Time to negative PCR test results
- Change from baseline in the 7-point ordinal scale

Cumulative:

- Cumulative incidence of serious adverse events (SAEs) or adverse events (AEs)

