#### **7.2.4.2. Data Analytic Models**

All secondary endpoint efficacy measurements available at post-baseline at scheduled measurements (Visits 2 through 5 [infusions 1 through 4] for exploratory markers and clinical labs; Visits 2 through 6 [infusion 1 through end of treatment] for chest X ray, CT scan, and ordinal scale score) will be analysed in a generalized linear mixed model. The model will predict each outcome as a function of the interaction between the fixed factors treatment group and time, controlling for lower order effects of time and treatment group. Models will control for stratification variables (see [Covariates and Other Strata](#)), and subject will be included as random effects. AEs/SAEs and AE severity will be analyzed as dichotomous outcomes (whether patient exhibited AE/SAE at any time during the study). AE/SAE attribution to study drug will be analyzed as count outcomes. All models will control for stratification variables.

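### SAP 5.5 can be read to shrink the AE/SAE comparison toward no difference, while SAP 7.1.4.1 and 7.2.4.1 point to a diffuse prior; the prior for this safety endpoint is unresolved

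*SAP*

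**What the plan says.** **Status of the endpoint.** In the protocol's Statistical Analysis, under Endpoints, and in the synopsis evaluation criteria: "Primary safety endpoints include incidence of adverse and serious adverse events". The protocol's lists of study endpoints also place cumulative AE/SAE incidence among the secondary endpoints. The SAP has it only as secondary: 7.2.1, within Secondary Efficacy Analyses, lists "Cumulative incidence of serious adverse events (SAEs) or adverse events (AEs").

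**The model.** SAP 7.2.4.2: "AEs/SAEs and AE severity will be analyzed as dichotomous outcomes", scored once per patient over the whole study and adjusted for the stratification variables. Attribution to study drug is modelled as a count. No prior is named there.

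**The regularising rule.** SAP 5.5: "Any secondary analyses for which issues of multiplicity might be a consideration will use weakly, informative priors to regularize all estimates". It continues: "Means for these regularizing priors will be centered on the null hypothesis, with variances determined by the scale of the data" and on credible effects from analogous studies. No numerical variance is given. As priors become more informative, 5.5 says, "the greater the degree of regularization, (2) the more conservative the estimates". Reports are to state the priors used for secondary analyses.

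**The competing rule.** SAP 7.1.4.1: "For all generalized linear models, priors for regression coefficients will be specified as" Normal with mean 0 and variance printed as 1×10, described as diffuse and neutral. SAP 7.2.4.1 says that secondary analyses follow the procedures of 7.1.4.1.

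**Population and descriptive reporting.** SAP 7.2.3 defaults secondary efficacy analyses to the Efficacy analysis set (all four infusions). SAP 5.7 and 8 put safety evaluations on the Safety analysis set (at least one infusion). SAP 8.1 tabulates treatment-emergent and serious AEs as patients, percentages and events.

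**The concern.** Shrinking toward zero is conservative for a benefit claim, because it makes a chance finding look smaller. For harm the direction reverses: the same prior moves the estimate toward no excess risk and pulls in the upper end of the interval, which is the end that matters for safety. The justification in 5.5 is written for efficacy and does not carry over. The protocol's safety null hypothesis is also that treatment does cause adverse events, so a prior centred on no difference sits on the favourable side of the protocol's own safety question.

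AE/SAE incidence sits in a secondary family with clinical laboratories, eight exploratory markers, imaging, PCR and the ordinal scale. An analyst could reasonably conclude that multiplicity is a consideration there and apply 5.5. Another could follow 7.1.4.1. Both would be following the SAP, and the harm estimates could differ materially. The synopsis says the trial should show whether the product is safe to give, so this choice should not be left until the data are in hand.

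**Working it through.** The documents give no power, event rate or detectable difference for AE/SAE incidence, and the protocol bases N on anticipated demand. There is no planned figure to reproduce beyond the split: 3:2 of 100 gives 60 and 40.

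**Step 1: which prior applies?**
- 5.5: conditional on a multiplicity concern; null-centred; no variance; no safety exemption.
- 7.1.4.1: all generalized linear models; Normal(0, variance 10). If an exponent was lost when the text was extracted, the prior is flatter still.
- 7.2.4.1: secondary analyses follow 7.1.4.1. Its double-exponential and horseshoe priors attach to additional cross-sectional analyses at each time point.
- 7.2.4.2: the AE/SAE model; silent.

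Nothing ranks these rules for AE/SAE incidence.

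**Step 2: how far could the estimate move?** Assumed data: SAEs in 12/60 v 4/40 (20% v 10%).

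Odds ratio = (12/48)/(4/36) = 2.25; log = 0.811.
Variance v = 1/12 + 1/48 + 1/4 + 1/36 = 0.382.

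For a Normal(0, s²) prior on the log odds ratio, the normal approximation gives a weight w = s²/(s² + v), posterior mean w × 0.811 and posterior variance w × v.

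| Prior on log odds ratio | w | Posterior odds ratio | Upper 95% limit | Pr(harm) |
|---|---|---|---|---|
| variance 10 (7.1.4.1) | 10/10.382 = 0.963 | exp(0.781) = 2.18 | exp(0.781 + 1.96×0.607) = 7.2 | 0.90 |
| SD 2.5 (assumed) | 6.25/6.632 = 0.942 | exp(0.764) = 2.15 | exp(0.764 + 1.96×0.600) = 7.0 | 0.90 |
| SD 1 (assumed) | 1/1.382 = 0.724 | exp(0.587) = 1.80 | exp(0.587 + 1.96×0.526) = 5.0 | 0.87 |
| SD 0.5 (assumed) | 0.25/0.632 = 0.396 | exp(0.321) = 1.38 | exp(0.321 + 1.96×0.389) = 2.9 | 0.80 |

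Grid posteriors for the logistic model agree to within about 0.1 to 0.2 on the odds ratio, depending on the intercept prior. All four intervals include 1, but the upper limit falls from about 7 to about 3 across the range of scales.

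**Step 3: effect on detection.** All binomial outcomes were enumerated at 60 v 40. Detection means Pr(odds ratio > 1) of at least 0.975; this cut-off is assumed, since the SAP sets none for harm. Event rates are also assumed; covariates and dropout are ignored.

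| True rates (placebo v active) | flat | variance 10 | SD 2.5 | SD 1 | SD 0.5 |
|---|---|---|---|---|---|
| 10% v 20% | 33% | 31% | 29% | 19% | 4% |
| 10% v 30% | 75% | 73% | 70% | 62% | 35% |
| 20% v 40% | 61% | 60% | 58% | 52% | 32% |

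These use an intercept prior of variance 1000. With a tighter intercept prior (SD 3.16), the 10% v 20% figures are 26% at variance 10, 18% at SD 1 and 4% at SD 0.5. At a cut-off of 0.75, 10% v 20% is flagged 77% of the time at variance 10, 74% at SD 1 and 64% at SD 0.5.

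**Step 4: how much is sample size?** Two-sided 5% test, 10% v 20%, ratio 1.5, pooled rate (0.1 + 1.5×0.2)/2.5 = 0.16.

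- Null term: 1.96 × √(0.16×0.84×(1 + 1/1.5)) = 1.96 × 0.473 = 0.928.
- Alternative SD: √(0.09 + 0.16/1.5) = 0.443.
- Power with 40 on placebo: Φ((0.1×√40 − 0.928)/0.443) = Φ(−0.67), about 25%.
- For 80% power: ((0.928 + 0.842×0.443)/0.1)² ≈ 169.2, so 170 placebo and 255 active, 425 in total.

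With no shrinkage at all, 100 patients are far short for this excess.

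**The case against.** A reader might infer that the SAP prescribes shrinkage for AE/SAE incidence. It does not. The trigger in 5.5 is conditional and names no safety analysis, and 7.1.4.1 claims all generalized linear models. The double-exponential and horseshoe priors probably do not reach this endpoint, since AE/SAE occurrence is scored once per patient and not at each visit. This part of the objection stands: coverage by 5.5 is a permitted reading, not a stated plan.

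A reader might also infer that, because of the prior, a real excess of harm would usually be missed. The documents do not support that. They set no harm threshold, 5.5 calls its priors weakly informative, and at SD 2.5 almost nothing is lost. For 10% v 20%, detection is low even with a flat prior. For 10% v 30% and 20% v 40%, it stays above 50% even at SD 1. The large losses need an SD near 0.5, which is a sceptical prior: 95% of its mass lies between odds ratios of about 0.38 and 2.7.

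Unshrunk data will also be shown. SAP 8.1 tabulates raw AE counts and percentages, and 7.2.2 gives unadjusted descriptive values, so a 12/60 v 4/40 imbalance would be visible. This mitigates the problem but does not remove it. Section 8.1 gives no between-arm estimate or interval. Its treatment-emergent window closes 3 days after the last infusion, with other AEs only listed, whereas the protocol collects AEs through day 28. The 7.2.4.2 model, which covers the whole study, is the SAP's only model-based arm comparison of AEs. Disclosing the prior afterwards is not pre-specifying it.

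Finally, the secondary listing began in the protocol, which gives AE/SAE incidence both labels. The point does not depend on blaming the SAP for that.

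**Conclusion.** The concern holds as a conflict between rules with a harmful direction under one reading. One rule could shrink the AE/SAE comparison toward no difference, another would leave it essentially unshrunk, and the SAP does not choose. The possible understatement runs from negligible (SD 2.5) to material (an odds ratio of 2.25 reported as roughly 1.75 to 1.8 at SD 1, or 1.35 to 1.4 at SD 0.5). Those scales, the event rates and the detection cut-off are assumptions; only the direction follows from the SAP text. The prior is not the main reason that small excesses would go undetected, and removing it would not cure that.

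A related conflict affects the same model. By its place in 7.2 it defaults to patients who received all four infusions, so anyone who died or stopped earlier would leave the AE comparison, contrary to 5.7 and 8.

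This should be corrected before analysis. It is a clarification with real consequences for the safety conclusion, not a fatal flaw.

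**What to change.** In SAP 5.5 and 7.2.4:
- Exclude the AE, SAE, AE-severity and drug-related-AE comparisons from the regularising priors of 5.5 and the shrinkage priors of 7.2.4.1.
- State that they use the diffuse coefficient prior of 7.1.4.1, naming the scale it applies to (log odds for the dichotomous models), on the Safety analysis set.
- Report the risk difference with its 95% credible interval, and read the upper limit as the excess risk that the data do not exclude.
- Show any shrunken estimate only as a sensitivity analysis, with the prior's centre and scale stated in advance.

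The cost is a few sentences and one table column. Intervals will be somewhat wider than under a regularising prior, which reflects what 60 and 40 patients can show. The report should also say that an interval including no difference is weak reassurance at this sample size.

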## **5.6. Interim analysis**

Interim analyses of primary and secondary efficacy data were not performed.

## 5.7. General Considerations

All continuous measurements will be summarised descriptively at each visit by treatment using observed data. Summary of continuous variables will be presented using N, Range, Mean (minimum, maximum), Standard Error of mean (SE), Standard Deviation (SD) (for normally distributed date), or Median and interquartile range (IQR) for non-normally distributed data. The categorical variables will be presented using number and percentage based on N.

For measurements over time, mean values will be plotted to explore the trajectory over time. Observed data will be used as the basis for plotting data along with bars as standard error (SE) or Standard Deviation (SD), if not otherwise specified.

The primary analytical approach will involve Bayesian statistical methods to assess the probability that an effect of HB-adMSCs 100mm exists (relative to placebo). Our analytical plan is shaped by the limitations of conventional (Frequentist) methods for addressing this question and the advantages of a Bayesian approach for assessing the probability that a given strategy might successfully be expanded into a larger-scale program for the treatment of COVID-19 symptoms. This data, valuable in its own right, can justify the commitment of resources needed for such an expansion. Further, current uncertainty regarding the probability of worse status on the inflammatory markers, change from baseline oxygenation, and time to return to room air (RTRA) as a function of HB-adMSC 100mm is readily incorporated in a Bayesian approach permitting more robust trial planning and design.

The Bayesian approach addresses these questions: (1) “Among patients with suspected COVID-19, what is the probability that allogeneic HB-adMSC 100mm confers benefit relative to placebo on status on inflammatory markers (C-Reactive protein, TNF-alpha, IL-6, IL-10), change from baseline oxygenation, and time to return to room air (RTRA) at treatment Day 10?” (2) “What is the best estimate of these effects?” and (3) “What is their precision?” By estimating the probability that such effects exist, we are assessing the probability that the alternative hypothesis is true; a probability that is, by definition, not accessible to Frequentist methods. The FDA has discussed the use of Bayesian statistical methods to make decisions regarding the efficacy of new treatments as an alternative to Frequentist methods in developing clinical applications. The current proposal will provide the optimal, unbiased estimates for the benefit conferred by allogeneic HB-adMSC, while also estimating the probability that such effects exist. Posterior distributions can then be used as informative priors for continued monitoring in expansions of treatments and treatment strategies exhibiting initial promise.

Presentation of results from the statistical models will include the estimated conditional/marginal mean treatment effects. For all endpoints analysed statistically, estimated mean treatment differences will be presented together with 95% credible intervals and posterior probabilities,

HB-adMSCs 100MM vs Placebo

All safety evaluations will be presented using Safety Analysis Set. The efficacy analysis will be presented using Efficacy analysis set.

Individual safety and efficacy parameters will be listed.

